## 2.1 Study Rationale

This trial is designed to demonstrate the superiority of MK-0653C (Ezetimibe/Atorvastatin combination tablet) 10/10 mg or 10/20 mg compare to a doubling dose of atorvastatin in LDL-C lowering effect in hypercholesterolemia participants not well controlled by statin monotherapy. The data from this trial will support the market authorization in China.

## 2.2 Background

MK-0653C is a fixed dose combination drug containing ezetimibe, a Niemann-Pick C1 Like 1 (NPC1L1) inhibitor, and atorvastatin, a HMG-CoA reductase inhibitor, as active ingredients. The active ingredients are ezetimibe 10 mg and atorvastatin 10 mg or 20 mg.

Refer to the Investigator's Brochure (IB)/approved labeling for detailed background information on atorvastatin, ezetimibe and MK-0653C.

### 2.2.1 Pharmaceutical and Therapeutic Background

Coronary heart disease (CHD), stroke and peripheral arterial disease caused by atherosclerosis are quite significant burdens to medical care in developed and developing countries [Barquera, S., et al 2015], and these diseases have taken the leading cause of death among both urban and rural areas in China [Yang, G., et al 2013]. The number of CHD incidence and mortality is rapidly increasing in recent 20 years in China [Zhou, M., et al 2016]. Considering the rapid aging speed in China, the future medical burden related to CHD will be even more critical. Blood cholesterol and the LDL-C are the independent risk factors to the CHD and ischemic stroke in Chinese cohort studies [Ren, J., et al 2010] [Li, Q., et al 2017]. Five large clinical studies: 4S, CARE, LIPID, WOSCOPS, and AFCAPS/TexCAPS have strongly established the base for statins to treat and prevent CHD progression by lowering TC and LDL-C. The following series studies, AVERT, LIPS, HPS, PROSPER, ASCOT, PROVE-IT, TNT, and IDEAL have demonstrated the benefit of statins to even acute coronary disease and multiple subgroup risky populations. Lower LDL-C became possible and gradually target for high risk and very high risk populations.

Statins have been introduced to China, and proved their efficacy on lowering LDL-C to 18-55% among Chinese patients. However, only 6-7% more reduction can be expected when doubling the doses if the LDL-C cannot be adequately controlled after initiation of statin monotherapy. Moreover, increasing statin dose is less efficacy in lipid control while adverse events of myopathy and liver function abnormality increased with dosing, especially in Chinese patients. In order to achieve the treatment goal and to further reduce the CHD risk, new medicines are introduced to China, within whom, ezetimibe is recommended to be selected as combined medicine with statins in clinical setting in China to enhance the efficacy while no more safety or tolerability issues [IMS Health 2006] [Grundy, S. M., et al 2004]. Combination of 10 mg ezetimibe with 10 mg atorvastatin or simvastatin may increase the rate of target achievement from around 18% to 72%, and the efficacy of combination use is similar to high dose (80 mg) of atorvastatin or simvastatin [Ballantyne, C. M., et al 2003] [Davidson, M. H., et al 2002] [Mikhailidis, D. P., et al 2009]. Therefore, China guideline

highly recommends using ezetimibe with low dose of atorvastatin to gain the similar effect. It also stated that there would be no additional risks of liver toxicity, myopathy or rhabdomyolysis when combining ezetimibe with statins compared to statin alone [Ballantyne, C. M., et al 2003] [Davidson, M. H., et al 2002] [Mikhailidis, D. P., et al 2009].

### **Significance of the Development of Fixed Dose Combination (FDC) Tablet for Therapy of Hyper-LDL-cholesterolemia**

- **Mode of action**

Ezetimibe inhibits the intestinal absorption of cholesterol and structurally-related phytosterols by blocking their passage across the intestinal wall. The molecular target of ezetimibe action has been identified as the putative cholesterol transporter NPC1L1. This blockade results in decreased absorption of dietary and biliary cholesterol without effects on the absorption of other lipids (e.g., triglyceride), lipid derivatives (e.g., bile acids) or lipidsoluble nutrients or vitamins.

Atorvastatin is a synthetic HMG-CoA reductase inhibitor. Atorvastatin and its metabolites, which show a similar level of activity, inhibit hepatic synthesis of cholesterol by selectively and competitively inhibiting HMG-CoA reductase in the liver, one of the main organs, that regulates the amount of cholesterol in the blood. As a result, atorvastatin increases the number of hepatic LDL receptors and inhibits lipoprotein secretion, thereby reducing the amount of lipids in blood [Haque, T. 2010].

Ezetimibe reduces hepatic cholesterol stores by inhibiting the absorption of cholesterol in the small intestine, but compensatory increased cholesterol biosynthesis occurs in the liver.

Coadministration of ezetimibe and an HMG-CoA reductase inhibitor which inhibits cholesterol biosynthesis was shown to complementarily lower cholesterol in studies in dogs and in hypercholesterolemic patients [Van Heek, M. and Davis, H. 2002] [Toth, P. P., et al 2010] [Grigore, L., et al 2008].

- **Adherence**

In a recent survey on adherence to statin treatment revealed a decrease in adherence with time; thus, statin treatment adherence is estimated to be about 50% in long-term therapy [Shroufi, A. 2010]. In addition, data on other diseases show that the treatment compliance rate is correlated with the number of tablets (capsules) prescribed [Ingersoll, K. S. and Cohen, J. 2008] [Cheong, C., et al 2008]. Therefore, a combination drug with a good tolerability profile in combination therapy for hyper-LDL-cholesterolemia may well be an important alternative as a treatment drug that can improve patients' treatment adherence and may be anticipated to display more reliable therapeutic efficacy. Consequently, concomitant administration of ezetimibe and statin is assumed to more effectively improve hyper-LDL-cholesterolemia based on their different mechanisms of actions.

## 2.2.2 Clinical Studies

### IMPROVE-IT Study

The IMPROVE-IT [Cannon, C. P., et al 2015] (Improved Reduction of Outcomes: Vytorin Efficacy International Trial) study was a multicenter, randomized, double-blind study, designed to establish the incremental clinical benefit and safety of ezetimibe (administered as part of ezetimibe/simvastatin Combination 10/40 mg tablet, a single tablet containing ezetimibe 10 mg and simvastatin 40 mg, if a participant had 2 consecutive LDL-C measurements  $>79$  mg/dL, then that participant was to have his/her simvastatin dose increased to 80 mg.) compared with simvastatin monotherapy in high-risk coronary artery disease participants and aims to address the question of whether the incremental reductions of LDL-C will translate into a clinical benefit. The study enrolled 18,144 high-risk participants with established coronary artery disease. At seven years, 32.7 percent of patients taking ezetimibe/Simvastatin experienced a primary endpoint event compared to 34.7 percent of patients taking simvastatin alone (hazard ratio of 0.936,  $p=0.016$ ). Based on the LDL-C range compared in the study's treatment arms (at one year, a mean LDL-C of 53 mg/dL versus 70 mg/dL, respectively), the 6.4 percent relative risk reduction observed in the ezetimibe/simvastatin arm in IMPROVE-IT was consistent with the treatment effect that had been projected based on prior studies of statins.

With regard to safety, there were no significant differences between treatment groups in adverse events of special interest in the trial, which included myopathy and rhabdomyolysis, gallbladder adverse events, liver enzyme elevations greater than or equal to three times the upper limit of normal, and cancer. These safety findings from IMPROVE-IT were generally consistent with current labeling for ezetimibe.

### MK-0653C Studies

Currently there are no clinical data available of combination administration of ezetimibe and atorvastatin in Chinese. However, there are clinical data globally on combination administration of ezetimibe and atorvastatin. The completed studies demonstrated the combination of ezetimibe and atorvastatin has superior LDL-C lower effect compare to the monotherapy of ezetimibe or atorvastatin. Especially in two add-on studies in patients whose LDL-C were not well controlled by atorvastatin treatment alone, adding ezetimibe 10 mg achieved bigger LDL-C level reduction compare to titrating up statin dose [Conard, Scott E., et al 2008] [Leiter, Lawrence A., et al 2008]. The safety of co-administration of ezetimibe and atorvastatin is comparable to ezetimibe or atorvastatin monotherapy. FDC has been shown to be bioequivalent to co-administration of ezetimibe and atorvastatin. Please refer to IB for the details.

## 2.3 Benefit/Risk Assessment

It cannot be guaranteed that participants in clinical studies will directly benefit from treatment during participation, as clinical studies are designed to provide information about the safety and effectiveness of an investigational medicine.

This is an active control study, and the study interventions have evidenced benefits for study predefined participants regardless of the randomization allocation. In addition, the study procedure, including dose selection and exclusion criteria, was well designed based on robust evidence in terms of safety profile of each component of study interventions from previous studies. And also study will be conducted according to GCP guidelines and highest regulatory requirement in order to ensure the wellbeing of all participants.

Additional details regarding specific benefits and risks for participants participating in this clinical study may be found in the accompanying IB and informed consent documents.

### 3 HYPOTHESES, OBJECTIVES, AND ENDPOINTS

All objectives and hypotheses will be evaluated in Chinese participants with hypercholesterolemia, inadequately controlled with 10 mg or 20 mg atorvastatin monotherapy.

Objectives	Endpoints
Primary	

Objective: To evaluate the percent change in LDL-C from baseline to Week 12 of MK-0653C 10/10 mg compared to atorvastatin 20 mg (Cohort A). Hypothesis: MK-0653C 10/10 mg is superior to atorvastatin 20 mg (Cohort A) in percent change from baseline in LDL-C to 12 weeks after treatment.

Objective: To evaluate the percent change in LDL-C from baseline to Week 12 of MK-0653C 10/20 mg compared to atorvastatin 40 mg (Cohort B). Hypothesis: MK-0653C 10/20 mg is superior to atorvastatin 40 mg (Cohort B) in percent change from baseline in LDL-C to 12 weeks after treatment.

 
Overall success is determined by a success on at least one hypothesis.
	

Low-Density Lipoprotein – Cholesterol (LDL-C) level

Objectives	Endpoints
Secondary	

Objective: To evaluate the safety and tolerability of administrated MK-0653C 10/10 mg and MK-0653C 10/20 mg once daily dosing through 12 weeks.

	

Adverse events

Laboratory parameters and vital signs

Study drug discontinuation

Exploratory	

Meeting LDL-C goal (yes, no)

LDL-C level

The level of total cholesterol (TC), HDL-C, non- HDL-C, triglyceride (TG) and Apo protein (Apo) B

\* The goal attainment values of LDL-C treatments across different ASCVD riskpopulations, detailed information can be found in [Table 13](#) of Appendix 7: 2016 Chinese guidelines for the management of dyslipidemia in adults.

## 4 STUDY DESIGN

[figure not shown]
### 4.1 Overall Design

This is a randomized, active-controlled, parallel-group, multi-site, double-blind study of MK-0653C in Chinese participants with hypercholesterolemia in order to support the marketing authorization in China.

This trial consists of a screening period, an atorvastatin active run-in period, a treatment period and a follow-up period, and the total duration for each participant will be approximately 21 weeks. Participants will enter the run-in period based on their use of statin at the time of screening. After run-in period, 180 participants for Cohort A and 270 participants for Cohort B will be enrolled for randomization.

Participant's eligibility will be assessed based on this risk category and randomization will be stratified according to the risk category as well. Participants diagnosed with elevated LDL-C who are currently treated with low to moderate dose of statins only and not at their target LDL-C goal will be screened up to 2 weeks for the eligibility. Demographic, medical history, lab test review and concomitant medication review or washout if necessary will be conducted. LDL-C treatment goal ([Table 13](#) in Appendix 7) is determined on the basis of the CV risk assessment result ([Figure 2](#)) which is evaluated based on the demographic characteristics, medical history and lipid profile according to current Dyslipidemia Management Guidelines in China: 2016 Edition.

\*Including smoking, low HDL-C, and men  $\geq 45$  years of age or women  $\geq 55$  years of age. The risk assessment and treatment of patients with chronic kidney disease refer to the treatment of dyslipidemia in special populations.

ASCVD: atherosclerotic cardiovascular disease; BMI: body mass index; CM: chylomicron; HDL-C: high-density lipoprotein cholesterol; IDL: intermediate-density lipoprotein; LDL-C: low-density lipoprotein cholesterol; TC: total cholesterol; TG: triglyceride; VLDL: very-low-density lipoprotein cholesterol.

Figure 2 The Risk Assessment Flow Chart

(adopted from Dyslipidemia Management Guidelines in China: 2016 Edition, referring to Appendix 7 for more details)

Participants who meet all eligibility criteria will be enrolled in a 5-week active run-in period after they discontinue the current statins with appropriate wash-out interval. Current statin is used to determine the allocation of different cohort: the participants who are currently treated at stable daily dose of 10 mg atorvastatin or other statin equivalent to or less than atorvastatin 10 mg will be assigned to Cohort A and will receive 10 mg atorvastatin during the run-in period; and the participants who are currently treated by atorvastatin at stable 20 mg or other statins equivalent to atorvastatin 20 mg will be assigned to cohort B and will receive 20 mg

atorvastatin during the run-in phase. The dose of other statins equivalent to atorvastatin can be found in [Table 3](#).

After the run-in period, the participants within either cohort who have not met their treatment goals for LDL-C according to their risk levels will be randomized into 2 cohorts to receive either MK-0653C or atorvastatin monotherapy (at twice the atorvastatin dose contained in MK-0653C) during a 12 weeks double-blind treatment period:

- Cohort A: Participants will be randomized to receive either MK-0653C 10/10 mg (containing ezetimibe 10 mg + atorvastatin 10 mg) or atorvastatin 20 mg in a 1:1 ratio;
- Cohort B: Participants will be randomized to receive either MK-0653C 10/20 mg (containing ezetimibe 10 mg + atorvastatin 20 mg) or atorvastatin 40 mg in a 1:1 ratio.

Participants who completed the trial or administered at least one dose of study intervention but prematurely discontinued will be followed by phone call 14 days after the last dose to assess serious adverse events (SAEs) and information will be documented on the follow-up visit page.

Specific procedures to be performed during the study, as well as their prescribed times and associated visit windows, are outlined in the SoA in Section 1.3. Details of each procedure are provided in Section 8.

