### 1.3 Schedule of Activities (SoA)

Study Period	Screening	Active run-in period (5 weeks)		Treatment (12 weeks)			Follow-up (14 days post last dose)	Notes
Visit Number/Title	Visit 1/ Screening	Visit 2	Visit 3	Visit 4/ baseline	Visit 5	Visit 6/ Discontinuation	Phone call	
Scheduled Hour, Day, Week, etc., and Window:	Week -7/-6	Week -5 (±7 days)	Week -1 (+3 days)	Week 0 (±3 days)	Week 6 (±7 days)	Week 12 (±7 days)	±3 days	The dates of Visit 3 and Visit 4 will be decided based on the date of Visit 2, while the dates of Visit 5 & Visit 6 will be decided based on the date of Visit 4.
Administrative Procedures								
Informed Consent	X							
Inclusion/Exclusion Criteria	X			X				
Participant Identification Card	X							The card will be updated once randomized.
Medical History	X							
Prior/Concomitant Medication Review	X	X	X	X	X	X		
Assignment of Screening Number	X							
LDL-C treatment target evaluation based on Cardiac Risk assessment	X							Based on Chinese Guidelines on Prevention and Treatment of Dyslipidemia in Adults (2016 Edition).
Monitor Dietary/Exercise Compliance	X	X	X	X	X	X		
Monitor Medication Compliance			X	X	X	X		
Assignment of Treatment/Randomization number				X				

Study Period	Screening	Active run-in period (5 weeks)		Treatment (12 weeks)			Follow-up (14 days post last dose)	Notes
Visit Number/Title	Visit 1/ Screening	Visit 2	Visit 3	Visit 4/ baseline	Visit 5	Visit 6/ Discontinuation	Phone call	
Scheduled Hour, Day, Week, etc., and Window:	Week -7/-6	Week -5 (±7 days)	Week -1 (+3 days)	Week 0 (±3 days)	Week 6 (±7 days)	Week 12 (±7 days)	±3 days	The dates of Visit 3 and Visit 4 will be decided based on the date of Visit 2, while the dates of Visit 5 & Visit 6 will be decided based on the date of Visit 4.
Run-in atorvastatin administration/dispensing		X						
MK-0653C/ Atorvastatin + matching placebo administration/dispensing				X	X			
Efficacy Procedures								
Lipid Panel A	X		X	X	X	X		LDL-C, total cholesterol (TC), HDL-C, non-HDL-C, and Triglyceride (TG). Blood sample should be drawn after at least 10-hour fasting. Otherwise the visit need to be rescheduled. Result of local lab within 4 weeks prior to Visit 1 can be used as reference for participant screening.
Apo protein (Apo) B				X	X	X		Blood sample should be drawn after at least 10-hour fasting. Otherwise the visit needs to be rescheduled.
Safety Procedures								
Full Physical Examination including height and weight	X			X		X		

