21	Agents potentially affect serum lipids	psyllium, other fiber-based laxatives, phytosterol margarine, herbal medicine and/or over the counter (OTC) therapies	8 weeks prior to V1	If the participant has been treated with a stable regimen for > 8 weeks prior to Visit 1 and agree to continue this regimen for the duration of the trial, concomitant therapy is acceptable.

Exclusion	Class	Details	Prohibition Start	Note
22	Anti-obesity drug	Mazindol	12 weeks prior to V1	
23	warfarin	Warfarin or warfarin-like anticoagulants and has not been on a stable dose with a stable INR.	V1	Warfarin or warfarin-like anticoagulants therapy is acceptable, if the participant must be on a stable dose with a stable INR for 6 weeks prior to Visit 1.
24	Lipid lowering agents	Cholestin TM, bile acid sequestrants, Ezetimibe, fibrates or niacin (>200 mg/day)	6 weeks prior to V1	
		Probucol	10 weeks prior to V1	
		Statin other than atorvastatin, Ezetimibe other than the ezetimibe component of MK-0653C	V1	

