### **8.11.2 Run-In (Visit 2 and Visit 3)**

Visit 2 will be performed approximately 5 weeks prior to randomization (Visit 4).

Dispense run-in intervention to a participant if he/she is eligible for study participation. Participants will be instructed to take 1 tablet from the bottle.

After initiating administration, participant who is determined to be not appropriate by the investigator will be excluded the study as screen failed. If a participant is not eligible for study participation, the investigator should contact with the participant, stop dosing study drug and performing the end of study visit immediately, and a safety follow-up visit by phone-call as appropriate.

*NOTE: it is not necessary for screen failed participant who did not start the study intervention to perform follow-up visit after the end of study visit.*

Approximately 4 weeks after Visit 2, participants will be scheduled to return for Visit 3. Blood lipid levels (e.g. LDL-C values) and biochemistry test measured at Visit 3 (Week -1) will be used to determine participant's eligibility for intervention allocation/randomization at Visit 4 (Day 1/Week 0).

Participant will be instructed on Chinese Guidelines on Prevention and Treatment of Dyslipidemia in Adults (2016 Edition), and will agree to maintain the diet/exercise regimen throughout the study.

No rescreening will be allowed of participants who discontinue during the run-in phase or fail to be eligible after the run-in phase.

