Statins are applicable for patients with hypercholesterolemia, mixed hyperlipidemia, or ASCVD. Currently, lovastatin, simvastatin, pravastatin, fluvastatin, atorvastatin, rosuvastatin, and pitavastatin are used in clinical practice in China. The cholesterol reduction levels have large differences depending on the different types and doses of statins. However, when any statin does is doubled, the continued reduction of LDL-C is only 6% (i.e., the so-called “rule of six of statin efficacy”). Statins can reduce TG levels by 7%-30% and increase HDL-C levels by 5%-15%.

Statins can be administered once per day at any time. However, the administration of LDL-C at night might be associated with higher levels of LDL-C reduction. After the expected efficacy of statin administration is obtained, the long-term administration should be continued. If patients can tolerate this treatment, then drug withdrawal should be avoided. Previous studies have suggested that statin withdrawal might increase the development of cardiovascular events. If adverse reactions occur after statin administration,then this treatment should be replaced with another type of statin, the dose should be reduced, and drug administration should be performed every other day; otherwise, other non-statin lipid lowering drugs should be used.

The analytic results of the Cholesterol Treatment Trials' (CTT) collaboration indicate that when LDL-C is reduced by 1 mmol/L after statin therapy in populations with different cardiovascular risk stratifications, the relative risk of major cardiovascular events is reduced by 20%, and allcause mortality is reduced by 10%, whereas the mortality caused by non-cardiovascular reasons does not increase. Current studies have repeatedly confirmed that the level of clinical reduction benefits of ASCVD by statins is linearly and positively correlated with the level of LDL-C reduction. The clinical benefits produced by statin therapy originate from the effect of LDL-C reduction. The levels of LDL-C reduction via different types and doses of statins are shown in [Table 15](#).

Table 15 The Cholesterol Reduction Intensity of Stains

High intensity (daily dose can reduce LDL-C by ≥ 50%)	Medium intensity (daily dose can reduce LDL-C by 25%-50%)
Atorvastatin 40-80 mg*	Atorvastatin 10-20 mg
Rosuvastatin 20 mg	Rosuvastatin 5-10 mg
	Fluvastatin 80 mg
	Lovastatin 40 mg
	Pitavastatin 2-4 mg
	Pravastatin 40 mg

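### Users of statins other than atorvastatin may be left without a statin between Visit 1 and Visit 2, for no scheduled purpose; a direct switch at Visit 2 would be a cheap wording fix

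*Combined protocol and SAP*

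**What the plan says.** Four parts of the protocol bear on this.

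- **Who may enter.** Inclusion criterion 2 (Section 5.1) and Table 3 admit people on simvastatin, lovastatin, pravastatin or fluvastatin at listed equivalent doses, as well as people on atorvastatin.
- **When the old statin stops.** Section 4.1 places the run-in "after they discontinue the current statins with appropriate wash-out interval". It also says of the screening period that "concomitant medication review or washout if necessary will be conducted". Neither place gives a length. Table 4 row 24 lists "Statin other than atorvastatin, Ezetimibe other than the ezetimibe component of MK-0653C" with prohibition starting at V1.
- **When the replacement starts.** The Schedule of Activities row "Run-in atorvastatin administration/dispensing" is marked at Visit 2 only, and Section 8.11.2 says: "Dispense run-in intervention to a participant if he/she is eligible for study participation". Section 6.5.1 specifies no rescue or supportive medication. No section tells sites to continue the old statin, or to prescribe atorvastatin, between Visits 1 and 2.
- **What the appended guideline says.** Section 10.1.1 of the guideline in Appendix 7 states: "If patients can tolerate this treatment, then drug withdrawal should be avoided". It adds: "Previous studies have suggested that statin withdrawal might increase the development of cardiovascular events".

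**The concern.** A site that follows Table 4 to the letter stops these four statins at Visit 1, before eligibility is settled, and has nothing from the study to give until Visit 2. The wash-out wording in Section 4.1 points the same way. Very-high-risk participants may be randomised (inclusion criterion 11c), so some of those affected may have established cardiovascular disease. If the old statin stops at Visit 1, people who later fail screening also interrupt treatment until failure is declared.

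What is at stake is a short and avoidable interruption of a tolerated drug, and the likelihood that sites will handle the switch differently. The efficacy result is not at stake.

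**Working it through.** **1. The plan's own duration.** Section 1.1 gives about 21 weeks in total: screening 2 + run-in 5 + treatment 12 + follow-up 2 = 21 weeks. This reproduces, with a 2-week screening phase.

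**2. The Visit 1 to Visit 2 interval (Schedule of Activities).** Visit 1 is Week -7 or -6, that is Day -49 or Day -42. Visit 2 is Week -5 ± 7 days, that is Day -35, range Day -42 to Day -28.

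- Nominal: 49 - 35 = 14 days, or 42 - 35 = 7 days.
- By the windows alone: shortest 42 - 42 = 0 days, longest 49 - 28 = 21 days.
- With the 2-week limit on screening (Sections 4.1 and 8.11.1): 0 to about 14 days.

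This is the longest time a participant could be off statin. It is not the time the protocol orders. That depends on the reading.

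**3. Time off statin under each reading.**

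- *Table 4 taken literally, nobody bridged:* the whole interval, nominally 7 to 14 days, allowed range 0 to about 14. Screen failures are off statin until failure is declared, because Section 6.5 applies its restrictions only during the ongoing study.
- *Section 4.1 read as eligibility first, then stop:* whatever the site judges appropriate, from 0 up to the same limit. Screen failures have no gap.
- *Old statin kept through screening, or local atorvastatin prescribed:* 0 days.

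**4. Does the gap serve a measurement?** Lipid Panel A is scheduled at Visits 1, 3, 4, 5 and 6, and chemistry at the same visits. Scheduled lipid or chemistry draws at Visit 2: 0. No off-statin value is collected at a scheduled visit.

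**5. Does the gap affect later data?** The schedule states: "The dates of Visit 3 and Visit 4 will be decided based on the date of Visit 2". From Week -5 to Week -1 is 4 × 7 = 28 days, and the +3-day window gives 28 to 31 days. Everyone in a cohort therefore has 28 to 31 days on the same run-in dose before the eligibility LDL-C, with or without a wash-out. Baseline at Visit 4 is nominally 5 × 7 = 35 days after Visit 2, and randomisation happens there.

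**6. What cannot be derived.** The documents give no figure for the number of participants on other statins, the LDL-C change over such a gap, or any effect on clinical events.

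**The case against.** The strongest reply is that nothing mandates a 7-to-14-day gap. A reader might infer one from Table 4, but the documents do not support it as a fixed requirement:

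- The bar at Visit 1 rests on one table cell. Exclusion criterion 24, which that row cites, does not name statins.
- The cell pairs other statins with ezetimibe from outside the study drug, which reads like a rule on concomitant use during the study.
- Section 4.1 sends people to the run-in once they meet the eligibility criteria, and allows wash-out during screening only where needed.
- The heading over the first inclusion criteria in Section 5.1 asks that they be met at both Visit 1 and Visit 2. This fits staying on a statin through screening, though it does not settle the matter, because the four stable weeks are counted back from Visit 1.
- Lead times in weeks are given for several other drug classes but not for statins, so an appropriate interval may be zero.
- Atorvastatin is not barred, so a site may bridge with a local prescription.

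All of this stands. It brings the lower end of the range to 0 days and makes the problem partly one of inconsistent wording. It does not remove the problem: Section 6.5 introduces Table 4 as specific restrictions, the cell says V1, and no section tells sites to bridge.

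A second reply concerns the guideline. Its advice follows a sentence about continuing long-term treatment once the expected effect has been reached. The sentence on events is hedged, and the title of the reference it cites concerns endothelial function after simvastatin withdrawal. This also stands. A reader might infer that the gap raises cardiovascular events; the guideline is only indirect support and does not show that for a short break before a switch.

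Third, safeguards exist. MI, PCI, CABG, unstable angina or stroke within 12 weeks is excluded, adverse events resulting from wash-out are reportable (Section 8.4.1), and local results from the previous 4 weeks can serve for screening (Appendix 2). These reduce the risk without closing the gap. Finally, Figure 1 is not available here and may give a reason for the wash-out; the readable text gives none.

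**Conclusion.** The point holds as a cheap improvement, a minor wording amendment. Table 4 row 24 and Section 4.1 permit, and on a literal reading of Table 4 require, users of four listed statins to be off statin for 0 to about 14 days before run-in atorvastatin is dispensed. The interval supports no scheduled measurement, and the protocol is inconsistent about whether it should occur.

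The safety cost is small and cannot be quantified from the documents. The upper limit assumes that Table 4 is applied literally, that nobody is bridged, and that the 2-week screening limit is kept.

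A reader might also infer that the gap distorts the Visit 3 LDL-C criterion or the comparison between arms. It does not: both follow at least 28 days on a common run-in dose, and randomisation comes after that.

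**What to change.** Set one rule: a direct switch at Visit 2.

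1. **Section 4.1.** Replace the wash-out phrase with a statement that the current statin continues at unchanged dose until the day before the first run-in dose at Visit 2. Limit the screening-period wash-out to prohibited drugs other than statins.
2. **Table 4, row 24.** Split the last line. Move the start for statins other than atorvastatin from V1 to the first run-in dose, and leave ezetimibe at V1. State that the participant's own atorvastatin also stops when run-in atorvastatin starts, so that the two are not taken together.
3. **Section 8.11.1.** Tell participants at Visit 1 not to stop their statin.

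The cost is wording in two sections and one table row. Eligibility criteria, visits, tests, sample size and eCRF do not change. The instructed gap becomes 0 days, and the 28 to 31 days of run-in before Visit 3 stay as they are. If the sponsor does have a reason for a wash-out, the protocol should state that reason and the length in days.
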